#### **Safety Outcomes:**

1. Death within 90 days\*#

2. Symptomatic ICH post-acute stroke treatment defined (As defined in the MOP)\*Indicates data collected in the QuICR registry # Indicates data collected in OPTIMISE registry

#### 5.10 How will the outcomes be measured at follow up?

The primary outcome (assessed using the modified Rankin Scale) will be determined by the Rankin Focused Assessment (RFA) method using centralized telephone interview by trained study personnel blinded to treatment allocation. The Rankin Focused Assessment consists of a 4-page form, accompanied by a 5-page Instructions. Details will be provided in the MOP.

Secondary outcome measures described above are all available through the QuICR and OPTIMISE registries and will be collected from those data sources. The home time outcome will be determined through linkage with administrative data to calculate the total time in the first 90 days after index event that a stroke patient is not an inpatient. Processes for administrative linkages within Alberta, Ontario and potentially other participating sites will be different based on local resources and policies. Return to baseline level of functioning will be determined using the same centralized telephone interview used to determine the primary outcome. Cognition will be assessed using an on-line assessment platform, with a login by Trial ID (no personal ID provided to the cognitive platform) and the cognitive data output to the trial database by Trial ID. These strategies and methods will be detailed in a manual of operations.

Primary safety outcomes death and symptomatic ICH will be collected through the trial database

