#### 5.9 Primary and secondary outcome measures

#### Primary Outcome: modified Rankin Scale 0-1 at 90 - 120 days

#### **Secondary Outcomes:**

- 1. Discharge destination (home, early supported discharge, rehabilitation facility, long term care, death) \* #
- 2. Home time (defined as number of days subject spends at home after index stroke event) 
- 3. Actual 90-120 day mRS score\*#
- 4. Door to needle time\*#
- 5. Door-in-door-out (DIDO) times at Primary Stroke Centres\*#
- 6. Recanalization status (mTICI score) at first angiographic acquisition in patients taken to the angio-suite for the purpose of administering EVT\*#
- 7. Proportion of patients administered EVT \*#
- 8. Door-to-groin puncture time in patients undergoing EVT\*#
- 9. CT-to-puncture time in patients undergoing EVT\*#
- 10. Return to baseline level of functioning
- 11. Cognition assessed via a brief, on-line cognitive assessment tool.

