- 2. Data on SAEs occurring within the first 24 hours including SAEs of special interest for the study, namely, a) symptomatic intracerebral hemorrhage (post-acute stroke treatment defined as per QuICR and OPTIMISE registries) b) angioedema and c) peripheral bleeding requiring blood transfusion will be collected through the trial database.
- 3. AEs measured routinely by the QuICR and OPTIMISE registries (highlighted as \* or # above) will be collected from those registries.
- 4. Administrative data linkages will be used to collect data on other AEs. The Canadian Discharge Abstract Database (DAD) captures all hospital separations for all Canadian provinces and

territories, with the exception of the province of Quebec. Each hospital discharge record includes up to 25 diagnosis codes, recorded using the ICD coding system, along with other clinical and demographic information. In addition, each diagnosis field in the database has an accompanying single digit field for the diagnosis type that is recorded whenever a diagnosis is recorded. The diagnosis type codes are as follows: type M: most responsible diagnosis; type 1: preexisting conditions (comorbidities) that influence care, or the hospital stay; type 2: conditions that arose after admission and that may thus represent complications of care; and type 3: preexisting conditions (comorbidities) that do not influence care, or the hospital stay. Type 2 diagnosis type codes will be used primarily to identify any AEs. Other data elements as relevant (interventions offered during admission; Group 11 or Blood transfusion given; Group 17) will also be collected. It will therefore not be possible to classify seriousness when data are obtained through administrative data linkages. Details on the data elements collected through DAD in each province will be made available in the MOP. The nature of the specific data linkages will be different in different jurisdictions (Alberta vs. Ontario). Data will be queried and obtained at regular intervals through the duration of the trial from the above data sources.

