	Adjusted logistic mixed-effects regression model with treatment (Tenecteplase vs Alteplase) as exposure; age, sex, baseline stroke severity, and stroke onset-to-needle time as fixed effects, and site, and registry (QuiCR vs. OPTIMISE) as random effects.
Ordinal mRS (blinded)	Ordinal logistic mixed-effects regression with treatment (Tenecteplase vs Alteplase) as exposure; for age, sex, baseline stroke severity, and stroke onset-to-needle time as fixed effects, and site, and registry (QuiCR vs. OPTIMISE) as random effects.
Return to pre-stroke status (pragmatic outcome) (blinded)	Risk difference and the corresponding 95%CI to assess non-inferiority. Risk ratio and the 95%CI to evaluate efficacy
	Adjusted logistic regression analysis with treatment (Tenecteplase vs Alteplase) as exposure; age, sex, baseline stroke severity, and stroke onset-to-needle time as fixed effects, and site, and registry (QuiCR vs. OPTIMISE) as random effects.
Euroqol 5-D Visual Analogue Scale (EQ5D-VAS) (blinded)	A linear mixed-effects regression model with treatment (Tenecteplase vs Alteplase) as exposure; age, sex, baseline stroke severity, and stroke onset-to-needle time as fixed effects, and site, and registry (QuiCR vs. OPTIMISE) as random effects.
EQ5D-5L (blinded)	Adjusted and unadjusted ordinal logistic regression analyses will be conducted for each EQ5D item (mobility, self-care, usual activities, anxiety, and depression) as the outcome variable.
	Health utility index derived from the EQ5D-5L items.
	Linear regression analysis with robust standard errors with treatment (Tenecteplase vs Alteplase) as exposure; age, sex, baseline stroke severity, and stroke onset-to-needle time as fixed effects,

Page 6 of 9

	Q
	and site, and registry (QuiCR vs. OPTIMISE) as
	explanatory variables.
Home time*	A generalized linear mixed-effects regression model with treatment (Tenecteplase vs Alteplase) as exposure; age, sex, baseline stroke severity, and stroke onset-to-needle time as fixed effects, and site, and registry (QuiCR vs. OPTIMISE) as random effects.
	In addition to home time, similar exploratory analysis will be conducted for other registry and administrative data outcomes such as length of hospital stay until discharge and discharge destination (home, home with home care, home with early supportive discharge, rehabilitation hospital, long term care and hospice) that will use appropriate regression analysis.
Mortality	Risk difference and the corresponding 95%CI

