#### 11. Missing data

Since the trial enrolls participants using a deferred consent approach, participants with missing mRS because of refusal of consent will be excluded completely from the analysis. Under the ITT principle, all remaining patients who are randomized are included in the analysis. Thus, every effort will be made to keep all missing data to a minimum i.e., < 5%. If, despite best efforts, there are missing data, then for the primary outcome analysis, data will be assumed to be missing completely at random (MCAR). Sensitivity analyses will be conducted to examine the impact of MCAR assumption on study conclusions using available case analysis and multiple imputation methods. Similarly, assumptions and missing data methods will be adopted for analysis of secondary outcomes.

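### Protocol 5.9 and 5.10 define home time differently, and the 5.10 rule, read literally, credits days after death and days in long-term care

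*Combined protocol and SAP*

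**What the plan says.** Protocol 5.9, secondary outcome 2: "Home time (defined as number of days subject spends at home after index stroke event"). 

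Protocol 5.10 turns this into a calculation. The source is linked data ("The home time outcome will be determined through linkage with administrative data"), and the quantity is to "calculate the total time in the first 90 days after index event that a stroke patient is not an inpatient". The section ends by leaving methods to a manual of operations, which is not part of the protocol or SAP.

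Protocol 5.11 describes the linked discharge database as one that "captures all hospital separations for all Canadian provinces and" territories apart from Quebec. It is a record of hospital stays.

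SAP section 9, home-time row, gives a generalized linear mixed-effects model with covariates. It gives no definition of the outcome and no value for patients who die. The same row lists discharge destinations ending in "rehabilitation hospital, long term care and hospice", without death. The protocol's list for that outcome ends in "rehabilitation facility, long term care, death".

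**The concern.** A programmer would code the 5.10 sentence, because it is the only one that says how to get a number. With a database of hospital stays, the natural code is 90 minus inpatient days. Unless a rule stops it, that code goes on counting after a patient has died, and it counts days in any facility that is not classed as inpatient.

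The score would then measure time out of hospital, not time at home. It would be wrong in direction for some of the sickest patients: an early in-hospital death would outrank a survivor with a longer stay. Home time is second on the protocol's list of secondary outcomes, and Protocol 6.6 foresees formal testing of secondary outcomes once non-inferiority is shown. A reader would take a higher mean as better recovery.

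**Working it through.** The documents give no expected home time, spread or power for this outcome, so there is no stated figure to reproduce. The check scores the same patients under both definitions.

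**Inputs from the documents**
- Window: 90 days (Protocol 5.10).
- Rule A, 5.10 read literally: 90 − inpatient days, with nothing removed after death.
- Rule B, 5.9 in its plain meaning: days alive and at home within the 90 days.

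**Assumptions (not in the documents)**
- Day of death d = 5 to 20.
- Inpatient stay had the patient lived, L = 5 to 60 days, followed by discharge home.
- Excess mortality in one arm: 2 percentage points.

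**Step 1: single patients**

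| Patient | Rule A | Rule B |
|---|---|---|
| Dies in hospital, day 5 | 90 − 5 = 85 | 0 |
| Home on day 14, survives | 90 − 14 = 76 | 76 |
| Home on day 30, survives | 90 − 30 = 60 | 60 |
| Home on day 14, dies on day 60 | 90 − 14 = 76 | 60 − 14 = 46 |
| Long-term care from day 20 | 90 − 20 = 70, if not counted as inpatient | 0 |

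**Step 2: effect of one extra death.** Compare the score with death against what the same patient would have scored alive.
- Rule A: change = max(0, L − d). Only inpatient days avoided count, and the change is never negative.
- Rule B: change = −(90 − max(L, d)). It is always negative over this range.

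**Step 3: effect on the arm mean of 2 points more deaths (0.02 × change)**

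| d | L | Rule A | Rule B |
|---|---|---|---|
| 5 | 5 | 0.02 × 0 = 0 | 0.02 × (−85) = −1.7 |
| 5 | 14 | 0.02 × 9 = +0.18 | 0.02 × (−76) = −1.52 |
| 5 | 60 | 0.02 × 55 = +1.1 | 0.02 × (−30) = −0.6 |
| 20 | 5 | 0.02 × 0 = 0 | 0.02 × (−70) = −1.4 |
| 20 | 60 | 0.02 × 40 = +0.8 | 0.02 × (−30) = −0.6 |

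Over the whole range, rule A moves the more lethal arm by 0 to +1.1 days and rule B moves it by −0.6 to −1.7 days. Rule A gives zero whenever death comes after the discharge that would have occurred anyway.

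**Scale of mortality.** The only 90-day death counts in the documents are from the cited Norwegian phase III trial (Protocol 5.11): (15 + 14)/549 = 5.3% and (14 + 12)/551 = 4.7%. Of those 55 deaths, 29 came by day 7. Protocol 4.3.4 expects more severe strokes here, so a higher rate is plausible, but no figure is given for this trial.

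**The case against.** The best defence is that nowhere does the plan say that days after death count as home time. Section 5.9 is the outcome definition, it cites a published home-time study, and a patient who has died spends no days at home. Section 5.10 can be read as naming the data source, with details left to the manual. The SAP's home-time row also carries an asterisk, and no footnote to it is visible in the text available. Either place may hold the missing rule. This stands in part: the crediting of days after death follows from the literal wording plus silence. It does not remove the problem, because 5.10 states a rule that conflicts with 5.9, and a general reference to a manual does not settle which one governs.

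Three stronger readings are tempting and are not supported.
- A reader might infer that a more lethal drug would score better. That needs days after death to be counted and deaths to cut short inpatient stays; otherwise the difference between arms is zero.
- A reader might multiply excess mortality by 90 minus the day of death, giving 0.02 × 70 = 1.4 to 0.02 × 85 = 1.7 days for 2 points. That compares each death with a score of 0, not with what the patient would have scored alive. The net figure is the 0 to 1.1 days shown above.
- A reader might extend the fault to length of stay and EQ-5D. The SAP does not say how in-hospital deaths enter length of stay, which it lists as exploratory. Its sentence in section 11, "Similarly, assumptions and missing data methods will be adopted for analysis of secondary outcomes", does not say that EQ-5D values after death are treated as missing. Those are gaps to ask about, not errors shown.

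**Conclusion.** The concern holds in a limited form. The two protocol sections define different quantities, and neither they nor the SAP score death or long-term care. Read literally, 5.10 yields an outcome that extra deaths cannot lower and can raise slightly: about 0 to 1.1 days on the arm mean per 2-point excess in mortality. That range rests on the assumed days of death and lengths of stay. The long-term-care result also depends on whether such facilities are classed as inpatient, which the plan does not say.

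It would be wrong to conclude that excess deaths could be hidden or that the main result is at risk. The primary analysis is the risk difference in mRS 0-1. The SAP analyses mortality by risk difference, Kaplan-Meier and adjusted regression, and the interim safety rule uses mortality itself. This is a secondary-outcome definition worth correcting, not a threat to the trial.

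**What to change.** Replace the 5.10 calculation, and state in the SAP's home-time row, one definition: days alive and living at home in the first 90 days after the index event, with 0 for days after death and for days in acute care, inpatient rehabilitation, long-term care or hospice. Align the SAP's discharge-destination categories with the protocol's list by including death. Settle both before any comparison by arm.

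The cost is one protocol sentence and a few SAP lines. Death and discharge destination are already collected. The downside is a little extra linkage work to date stays in facilities.

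### Protocol 5.10 calculates home time as time not spent as an inpatient, which taken literally credits days after death and days in long-term care as days at home

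*Combined protocol and SAP*

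**What the plan says.** Protocol 5.9 lists the secondary outcome as "Home time (defined as number of days subject spends at home after index stroke event", with a citation for the measure. It gives no time window and no value for patients who die. The same list has discharge destination as a separate outcome, "Discharge destination (home, early supported discharge, rehabilitation facility, long term care, death", so long-term care and death are treated there as states other than home.

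Protocol 5.10 gives the data source, "The home time outcome will be determined through linkage with administrative data", and the rule, which is to "calculate the total time in the first 90 days after index event that a stroke patient is not an inpatient". It leaves further detail to a manual that is not among the documents.

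The home time row in the outcome table of SAP section 9 specifies "A generalized linear mixed-effects regression model with treatment (Tenecteplase vs Alteplase) as exposure", with covariates and random effects. It contains no definition, no window and no value for deaths. The row label carries an asterisk, but no matching note appears in the available text.

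**The concern.** The two protocol sections do not measure the same thing. The complement of inpatient time is wider than time at home: it takes in every day after death and every day in long-term care. Only 5.10 can be programmed as written.

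The serious part is the treatment of death. A death early in the admission uses few inpatient days and so scores close to 90. The worst outcome then gets nearly the best score, and a mortality difference between the arms can move home time the wrong way or barely move it at all. Protocol 6.6 places secondary outcomes under hierarchical error control once non-inferiority is shown, and SAP section 9 tests them at 0.05, so the result would be reported with some weight.

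**Working it through.** The documents give no effect, standard deviation or power for home time, so there is no stated figure to reproduce. The check applies the 5.10 rule arithmetically.

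**Single patients.** Score = 90 - inpatient days.

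- Death in hospital on day 1, 3, 7 or 30: 89, 87, 83 or 60 days.
- Discharge home after 7, 14 or 30 inpatient days: 83, 76 or 60 days.
- Move to long-term care on day 14: 76 days, the same as going home on day 14.

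**Arm means.** Let m be mortality, d the day of in-hospital death and L the survivors' mean inpatient days. None of these is in the documents; all are assumptions.

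- 5.10 rule: mean = (1 - m)(90 - L) + m(90 - d). Raising mortality by Δm changes the mean by Δm × (L - d).
- Deaths scored zero: mean = (1 - m)(90 - L). The change is -Δm × (90 - L).

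Under the 5.10 rule the sign therefore depends only on whether d is smaller than L. For Δm = 0.05, the change in mean days is:

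| | L = 10 | L = 20 | L = 30 | L = 45 |
|---|---|---|---|---|
| 5.10 rule, d = 3 | +0.35 | +0.85 | +1.35 | +2.10 |
| 5.10 rule, d = 7 | +0.15 | +0.65 | +1.15 | +1.90 |
| 5.10 rule, d = 14 | -0.20 | +0.30 | +0.80 | +1.55 |
| Deaths scored zero | -4.00 | -3.50 | -3.00 | -2.25 |

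The one cell without a reversal (d = 14, L = 10) still shows -0.20 where scoring deaths as zero gives -4.00.

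**Illustration with 3 points.** Take mortality of 15% against 18%, survivors averaging 60 days (L = 30) and deaths credited 80 days (d = 10).

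- 5.10 rule: 0.85 × 60 + 0.15 × 80 = 63.0, and 0.82 × 60 + 0.18 × 80 = 63.6. Difference +0.6 days.
- Deaths scored zero: 0.85 × 60 = 51.0, and 0.82 × 60 = 49.2. Difference -1.8 days.

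**Long-term care.** If 5-10% of patients spend about 60 days there (assumed), the rule adds 0.05 × 60 = 3 to 0.10 × 60 = 6 days to each arm's mean.

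**Are early deaths plausible?** The NOR-TEST table in protocol 5.11 lists 15 + 14 = 29 deaths up to day 7 and 14 + 12 = 26 in days 8-90. So 29 of 55 (53%) fell in the first week, and each would be credited at least 83 days.

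**The case against.** The strongest reply is that nothing in the documents says outright that days after death count. Section 5.9 speaks of days at home, and a dead patient has none. The manual, the cited reference or a note behind the SAP asterisk may settle the matter. It is true that the crediting of days after death follows from the literal rule together with silence elsewhere. But 5.10 states an explicit calculation, and sources that are not in the documents cannot be relied on to overrule it.

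The second reply is that the effect is small. With an assumed standard deviation of 25-35 days and 800 patients per arm, the standard error of the difference is SD × √(2/800), or 1.25-1.75 days. An artefact of 0.6 days would not by itself give a convincing result for the more lethal arm. That stands. The loss of a true negative difference is the larger part: the gap between -1.8 and +0.6 is 2.4 days.

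The third is that death within 90 days is a safety outcome with its own analysis and its own interim stopping guidance, and that the SAP wording beside the home time row suggests exploratory status. This also stands, and it limits the importance of the point. A mortality signal could not be hidden by this variable.

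A reader might also infer that a patient whose record fails to link would score the full 90 days. The documents do not say so. The linkage appendix offers an account of lost records for chart review, protocol 7.4 has linkage quality checked, and SAP section 11 extends missing-data methods to secondary outcomes.

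**Conclusion.** The conflict between 5.9 and 5.10 is real, and the available SAP text does not resolve it. Taken literally, the 5.10 rule credits days after death and days in long-term care as home days. Facility days are clearest for long-term care, since inpatient rehabilitation may count as inpatient in the linked data.

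It would be tempting to say that more deaths always improve the score. They do so only when deaths use fewer inpatient days than survivors. Besides the -0.20 cell, the reversal also fails if survivors average 65 home days, long-term care adds 6 days per arm (6/0.85 = 7.06 per survivor, giving 72.06) and deaths are credited 70: 0.03 × (70 - 72.06) = -0.06 days. Even then the harm is almost erased, since scoring deaths as zero gives -0.03 × 65 = -1.95.

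The sizes rest on assumed mortality, timing of death and length of stay, and on the extra deaths being drawn from average survivors. NOR-TEST mortality was about 5% (29/549 and 26/551), below the 15% used here, though in milder strokes. The baseline level does not alter the difference; the assumed excess does. Home time plays no part in the non-inferiority decision. The rule should be corrected before analysis, but it does not threaten the primary result.

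**What to change.** Put one definition in protocol 5.10 and in the SAP home time row: the number of days from the index event to day 90 on which the patient is alive and living at home. Count zero for every day in hospital and every day after death. Do not count days in long-term care or another facility as home where discharge destination or linked data identify them. State how later moves between facilities are handled when the linked data do not capture them.

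The death correction costs a sentence in each document and some programming. Protocol 5.10 already collects deaths in the trial database, and the Kaplan-Meier analysis in the SAP needs their timing.

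The facility part may cost more. Discharge destination is recorded in both registries, but only at discharge. The Discharge Abstract Database "captures all hospital separations for all Canadian provinces and" territories other than Quebec, and the documents do not show that any source dates facility moves after first discharge. If none does, the SAP should say so as a stated limitation of the outcome.

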#### 5.3 Proposed practical arrangements for allocating participants to trial groups

Eligible patients will be randomized in a 1:1 ratio. Randomization will use a validated minimal sufficient balance (MSB) algorithm, to assure balance by site. The algorithm will kick in after the site has enrolled 5 subjects. The standard distribution is 50-50, but when an imbalance is detected with a p-value less than 0.3, the distribution changes to 65-35 in the direction against the imbalance. Randomization will be centralized, secure and concealed using a real-time web-based server, thus eliminating the possibility of confounding due to allocation bias. The central server will be linked to a randomization mechanism and will only be able to allocate one patient to either arm of the trial at one time. Investigators will be able to rapidly access the randomizer through a secure internet web browser or secure automated phone number or text message. Investigators will have to enter a site-specific ID number followed by an Investigator specific ID number and the weight of the patient in kilograms. They will then receive the drug allocation (tenecteplase vs. alteplase) along with unique study subject ID and the calculated drug dosage. They will later be prompted to enter if a) the correct drug was administered b) the correct dose was administered and c) the vial LOT number and expiry date of the administered drug.

Emails will be sent from the central trial server to site investigators and trial personnel with the site ID, unique study subject ID and drug allocation (study enrolment form). A copy of this email can be

printed and included in the patient chart. In addition, this email will also have a PDF checklist reminding site co-ordinators to ensure the following

- 1. The study enrolment form is placed in the clinical patient chart
- 2. The patient and surrogate contact information is documented in the checklist
- 3. Consent is obtained (see section 5.4) and documented in the study database
- 4. The unique study subject ID and registry ID are entered in the study database
- 5. Report any serious adverse events occurring within the first 24 hours of randomization. This information will be documented on paper and/or in the study database

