#### 5.5 Proposed methods for protecting against sources of bias

The trial will have allocation concealment and blinded endpoint assessment. Given the time sensitive nature of acute stroke treatment, blinding the enrolling health personnel and patient to treatment allocation is not practical. Primary clinical outcome data (assessed using the modified Rankin Scale) will be determined by the Rankin Focused Assessment (RFA) method using centralized telephone interviews conducted by central trial personnel blinded to treatment allocation. The trial coordinator may contact the site to help schedule phone follow-ups. Follow-ups will be scheduled 90 to 120 days after randomization. The manual of procedures (MOP) will describe in detail the Rankin Focused Assessment method for use by central trial personnel.

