## 8. Blinding

Treatment assignment is open label. Blinding of the outcome assessment at 90-120 days will be ensured by having central personnel trained on administration of the Rankin Focused Assessment, blinded to treatment allocation, and not involved in the acute treatment period conduct the assessment via telephone.

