	A Kaplan-Meier survival distribution. Patients alive after 90/120 days were censored. Logistic mixed-effects regression model with treatment (Tenecteplase vs Alteplase) as exposure; age, sex, baseline stroke severity, and stroke onset-to-needle time as fixed effects, and site, and registry (QuiCR vs. OPTIMISE) as random effects.
Symptomatic intracerebral hemorrhage	Risk difference and the corresponding 95%CI
	Logistic mixed-effects regression model with
	treatment (Tenecteplase vs Alteplase) as
	exposure; age, sex, baseline stroke severity, and
	stroke onset-to-needle time as fixed effects, and site, and registry (QuiCR vs. OPTIMISE) as random effects.
Intracranial Hemorrhage on follow-up Imaging (Blinded)	Difference in proportion of ICH categories and the corresponding 95%Cl

Page **7** of **9** 

 
Parenchymal hemorrhage (hemorrhagic infarction type 1, hemorrhagic infarction type 2, parenchymal hematoma type 1, parenchymal hematoma type 2, remote hemorrhagic infarction type 1, remote hemorrhagic infarction type 2, remote parenchymal hematoma type 1, remote parenchymal hematoma type 1, remote parenchymal hematoma type 2)
 
Subdural hemorrhage
 
Subarachnoid hemorrhage
 
Intraventricular
 
	
Peripheral Bleeding requiring Blood Transfusion	Risk difference and the corresponding 95%CI
Angioedema	Risk difference and the corresponding 95%Cl
Proportion of patients receiving EVT	Risk difference and the corresponding 95%CI.
	Logistic mixed-effects regression model with
	treatment (Tenecteplase vs Alteplase) as
	exposure; age, sex, baseline stroke severity, and
	stroke onset-to-needle time as fixed effects, and site, and registry (QuiCR vs. OPTIMISE) as random effects.
Other SAEs and SUSARs	Risk difference and the corresponding 95%CI

Page **8** of **9** 

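### Symptomatic ICH is site-reported in an open-label trial with no blinded confirmation described, and the blinded imaging read already in the SAP is not linked to it

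*Combined protocol and SAP*

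**What the plan says.** **Allocation is known at the site.** Protocol 5.5 states that "blinding the enrolling health personnel and patient to treatment allocation is not practical", and SAP 8 that "Treatment assignment is open label". Under protocol 5.3, "Emails will be sent from the central trial server to site investigators and trial personnel", giving the study ID and the drug. The same email carries a checklist for site co-ordinators. Its first item puts the enrolment form in the clinical chart, and a later one reads "Report any serious adverse events occurring within the first 24 hours of randomization".

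**Source of symptomatic ICH.** Protocol 5.10: "Primary safety outcomes death and symptomatic ICH will be collected through the trial database". Protocol 5.11 also routes 24-hour events, symptomatic ICH among them, through the trial database. The lists in 5.9 and 5.11 mark it as held in both registries too.

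**What is blinded.** Protocol 5.5 and 7.4 (item 6) and SAP 8 specify blinded assessors for the 90-120 day assessment. Item 7 of protocol 7.4, on safety data, has no blinding provision. The SAP 9 table labels blinding row by row: the mRS rows, return to pre-stroke status and the EQ-5D rows carry the label, as does "Intracranial Hemorrhage on follow-up Imaging (Blinded"). The symptomatic ICH row does not.

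**Definition.** Protocol 5.9 has "Symptomatic ICH post-acute stroke treatment defined (As defined in the MOP"), and SAP 9 also points to the manual of procedures (MOP). Protocol 5.11 has "symptomatic intracerebral hemorrhage (post-acute stroke treatment defined as per QuICR and OPTIMISE registries"), and the synopsis likewise points to the registries.

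**The concern.** Calling a hemorrhage symptomatic usually involves judgement about whether a deterioration is due to the bleeding. When the person reporting can see the allocation, that judgement can differ between arms. Death, the other key safety outcome, is little open to this problem, so symptomatic ICH is where masking would help most.

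The SAP already plans to obtain masked information on part of the event, namely whether there is hemorrhage and of what type, but analyses it only as a separate outcome. Two documentary sources for the definition leave further room for sites to differ.

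At stake is whether a finding of non-inferior efficacy can be read as coming with similar harm. With few events, differential labelling of a handful could create or hide part of a difference.

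**Working it through.** **1. Which steps are masked, according to the documents**

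| Step | Masked? | Source |
|---|---|---|
| Treatment and in-hospital care | No | Protocol 5.5, SAP 8 |
| Decision to obtain a follow-up scan | No; standard care only | Protocol 5.2.2 |
| Clinical worsening and event report | No masking described; sites hold the allocation | Protocol 5.3, 5.10, 5.11 |
| Hemorrhage type on follow-up imaging | Yes | SAP 9 table |
| Confirmation of symptomatic ICH | None described | Protocol 5.9-5.11, SAP 9 |
| Trial Safety Committee review | No; unblinded data | Protocol 5.11 |

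The one masked step is not used in the symptomatic ICH analysis.

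**2. The plan's own figure**

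The documents give no power or precision figure for symptomatic ICH. The only stated calculation is for the primary outcome (protocol 6.1: 35% and 38%, margin 5 points, one-sided 2.5%, 90% power):

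n per arm = (1.960 + 1.282)² × (0.35×0.65 + 0.38×0.62) / (0.03 + 0.05)² = 10.507 × 0.4631 / 0.0064 ≈ 760.3, so 761 against 759 stated.

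Allowing 5% loss: 2 × 759 / 0.95 ≈ 1598, which fits 1600, or 800 per arm. Nothing in this point changes that.

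**3. Sensitivity of the symptomatic ICH difference**

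Inputs: 3.2% with alteplase and 3.3% with tenecteplase (meta-analysis cited in protocol 4.5.1); 800 per arm.

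- Expected events: 0.032 × 800 = 25.6 per arm.
- 95% half-width: 1.96 × √(2 × 0.032 × 0.968 / 800) = 1.96 × 0.0088 = 1.72 points.
- 5 events reclassified in one arm (assumed): 5/800 = 0.63 points, or 0.63/1.72 ≈ 36% of the half-width.
- 10 events (assumed): 10/800 = 1.25 points, still inside the half-width.

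The event rate is also uncertain. The earlier phase III trial tabulated in protocol 5.11 had 15/549 = 2.7% and 13/551 = 2.4%, so a range of 2% to 5% is shown:

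| Rate | Events per arm | Half-width (points) | 5-event shift as share of half-width |
|---|---|---|---|
| 2% | 16 | 1.37 | 46% |
| 3.2% | 25.6 | 1.72 | 36% |
| 5% | 40 | 2.14 | 29% |

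**4. The same shift as a false-positive rate**

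Assume a true rate of 3.2% in both arms and 20% under-reporting in one arm (about 5 events). The observed rates become 3.2% and 2.56%, a shift of 0.64 points.

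SE = √[(0.032×0.968 + 0.0256×0.9744)/800] = 0.00836, and 0.0064/0.00836 = 0.77 standard errors.

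The chance of a nominally significant difference is then about 12% instead of 5%. At 10% under-reporting it is about 7%, and at 30% about 22%. The documents give no misreporting rate, so these figures show sensitivity only.

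**The case against.** The strongest reply is that this rests on silence. The MOP holds the definition and the outcome methods and was not available for this review; it may contain a central confirmation step. That stands, so the claim is limited to what the protocol and SAP describe. If the MOP has such a step, one sentence in the SAP closes the point.

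Second, the planned read addresses the more objective part of the event. It cannot settle clinical worsening, and scans are ordered by unmasked clinicians. Confirmation can discount or retype reported events but cannot recover events never reported. That also stands. A reader might infer that the bias could be removed; the documents support only a reduction.

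Third, the SAP gives the read little more than its blinded label. It does not say which patients it covers or when results arrive, and neither document costs the work, so a claim that the change is cheap has no figure behind it. What can be said is that it reuses a read already planned.

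Fourth, a reader might infer any of the following, none of which the text supports:
- that the people who gave the drug report the event. Protocol 5.3 assigns reporting to site co-ordinators and 7.2 has registry or health-service staff entering QuICR data. Access to the allocation is a fair inference for site staff; having administered the drug is not stated.
- that the bias favors tenecteplase. Protocol 4.4 calls it potentially safer but also notes less experience with it in stroke, and 4.3.4 reports slightly more symptomatic ICH with it at a higher dose. No direction is established.
- that the plan breaks a promise. Blinded assessment is specified for the 90-120 day assessment, and protocol 7.4 ties blinded ascertainment to the primary outcome.

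Finally, symptomatic ICH has no margin, and the stated safety stopping rule uses mortality. Mortality, the blinded ordinal mRS and the blinded hemorrhage categories also inform harm. This limits the consequence but does not answer the point: SAP 9 still names symptomatic ICH as a key safety outcome.

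**Conclusion.** The point holds in limited form. A key safety outcome is reported by sites with access to the allocation, no blinded confirmation is described, and a planned masked read that covers part of the event is left unconnected. The definition is also referred to two different sources.

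The size is illustrative: about 0.6 points for 5 reclassified events, against a half-width of 1.7 points. It assumes a 3.2% rate, 800 per arm, reclassification confined to one arm, and no confirmation step in the MOP. The documents neither show that such misclassification would occur nor say which arm it would favor. The efficacy conclusion, sample size, alpha and power are untouched.

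**What to change.** In SAP 9:

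1. Pre-specify an analysis of symptomatic ICH in which the hemorrhage of each reported event is confirmed and typed from the planned blinded imaging read. Count events with no available image as reported.
2. Give the as-reported count by arm alongside it, with the number of reported events that were confirmed, not confirmed, or without an image.
3. State one definition of symptomatic ICH in the SAP, and reconcile protocol 5.9 and SAP 9 (MOP) with the synopsis and protocol 5.11 (registries).
4. If the MOP already contains blinded confirmation, say so and describe it.
5. Acknowledge that clinical worsening and the decision to scan remain unblinded.

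The cost is SAP wording and matching about 50 reported events (2 × 25.6 at 3.2%) to their reads. Querying unreported parenchymal hematomas with allocation masked would address missed events as well, but adds work of unknown size and is optional.
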